### 2.7.1 Adverse events (AEs)

The missing onset date of AE will be imputed using the Novartis standard imputation rules (Section 5.1.2).

The Medical Dictionary for Regulatory Activities (MedDRA) version 25.0 or later will be used to code Adverse Event (AE) to a SOC and a PT. The version used will be displayed in the table footnote.

The number (and percentage) of participants with AEs will be summarized by following approach as defined in Table 2-6, in terms of all AEs, Serious Adverse Events (SAEs), treatment-related AEs or SAEs and fatal AEs that caused death:

- by treatment arm, primary system organ class and preferred term
- by treatment arm, primary system organ class, preferred term and maximum severity
- by treatment arm, preferred term with most frequency (incidence rate > 10%)

**Table 2-6 AE summaries**

Category	by SOC and PT	by SOC, PT and maximum severity	by most frequent PT (≥ 10%)
All AEs	Y	Y	Y
SAEs	Y		
All treatment-related AEs	Y	Y	
Treatment-related SAEs	Y		

For all AE tables presented by SOC and PT, the SOCs will be presented in alphabetical order and PTs will be ordered within the SOC by decreasing order of frequency. AE tables by preferred term only will be sorted in descending order of frequency.

A participant with multiple adverse events within a primary system organ class is only counted once towards the total of the primary system organ class. If a particular AE severity is missing, the variable will be listed as missing and treated as missing in summaries. If a participant reported more than one AE within the same SOC, the participant will be only counted once and the AE with greatest severity will be presented. Similar approach will be used to handle the situation of multiple AE within the same PT for the same participant.

The time to onset of AEs will be summarized by PT by descriptive statistics.

All AEs and SAEs will be listed separately at individual level and by treatment arms.

Participants with any abnormal findings (worsening or newly occurring) in AE will be listed by treatment arms. This listing is used to evaluate the withdraw/rebound effect of MIJ821 after 2 weeks of the treatment. A ‘newly occurring AE’ is defined as an AE that did not happen between treatment on Day 1 and the 2 weeks follow-up afterwards but happened after 2 weeks. A ‘Worsening AE’ is defined as an AE happened between treatment and 2 weeks in follow-up, and the severity increased after 2 weeks. Note that the actual Day 15 visit time will be used for the 2-week cut-off time point.

### 2.7.1.1 Clinical trial safety disclosure

For the legal requirements of ClinicalTrials.gov and European Union Drug Regulating Authorities Clinical Trials (EudraCT), following summaries listed in [Table 2-7](#) will be provided.

**Table 2-7 Safety disclosure requirements**

	Requirements	CT.GOV	EudraCT
SAE	Number of subjects who had treatment emergent / on-treatment SAE	Y	Y
	Number of subjects who had on-treatment death	Y	Y
	Number of subjects who had on-treatment death due to SAE that were causally related to treatment		Y
	Number of SAEs by SOC/PT	Y	Y
	Number of occurrences of SAEs by SOC/PT		Y
	Number of occurrences of SAEs that were causally related to treatment by SOC/PT		Y
	Number of SAEs, with outcome of death, related to treatment/all by SOC/PT		Y
NSAE	Number of subjects who had treatment emergent / on-treatment Non-SAE with 0-5% threshold	Y	Y
	Number of Non-SAEs (0-5% threshold) by SOC/PT	Y	Y
	Number of occurrences of Non-SAEs with 0-5% threshold by SOC/PT		Y

### 2.7.1.2 Adverse events of special interest / grouping of AEs

The Adverse Events of Special Interest (AESI) is based on the availability of incremental clinical experience with MIJ821 and identified during safety review in electronic Compound Case Retrieval Strategy (CRS). MedDRA search criteria for AESIs will be identified by the latest version of CRS.

AESI will be summarized by risk and by PT for each treatment arm for the on-treatment period.

In addition, the investigator reported AESIs from the eCRF will be summarized similarly by risk and by PT and treatment arms.

The time to onset (starting from dosing on Day 1) and time to resolution (starting from first onset date) of each AESI will be summarized by descriptive statistics. Separate summary tables will be provided for AESIs started on dosing day (within 24 hours post-dose) and overall. In the case if a patient has multiple AESIs, the earliest starting time will be summarized for onset time and the latest end time will be used in summary of resolution time for that patient. The dot plot based on the onset time of each AESI at individual patient level will be provided for AESIs started on dosing day (within 24 hours post-dose) and overall.

Listing of the above AESI will be provided at participant level and by treatment arms for both AESIs identified by CRS and investigator reported, separately.

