1.2 Purpose

The main purpose of this non-confirmatory study is to evaluate the safety and efficacy of a single s.c. MIJ821 injection in addition to standard pharmacological antidepressant (SoC) treatment in participants suffering from TRD assessed by the MADRS (Montgomery and Asberg 1979), a validated and widely employed scale in depression trials, evaluated 24h after study drug administration.

Furthermore, it is expected that this study will provide information about the dose-response and exposure-response relationship of the antidepressant effect of MIJ821 after single s.c. injection, which will be used to guide dose selection for confirmatory studies.

2 Objectives, endpoints and estimands

Table 2-1 Objectives and related endpoints

Objective(s)	Endpoint(s)	
Primary objective(s)	Endpoint(s) for primary objective(s)	
• To assess efficacy of MIJ821 (versus placebo) in treatment resistant depression after single s.c. injection	MADRS total score at 24 hours after s.c. injection compared to baseline assessment	
Secondary objective(s)	Endpoint(s) for secondary objective(s)	
To assess safety and tolerability of MIJ821 after single s.c. injection	 Incidence and severity of treatment-emergent adverse events (TEAEs), including AEs of special interest; standard safety assessments such as vital signs, ECG, hematology, blood chemistry, urinalysis; Clinician-Administered Dissociative States Scale 	

Objective(s) Endpoint(s) (CADSS) score, Modified Observer's Assessment of Alertness/Sedation (MOAA/S), C-SSRS, memory assessment using orientation questions, results of local tolerability assessments • PK properties of MIJ821 in plasma described by • To assess MIJ821 PK in plasma after single s.c. injection Area under the curve from time zero to time of last measurable concentration (AUClast), maximum plasma drug concentration (Cmax), time to reach maximum plasma concentration (Tmax) (parameters not limited). • To assess the duration of antidepressant effect of • MADRS total score at Day 8, 15, 22 and 29 visits MIJ821 compared to baseline • To characterize the dose-response and exposure-• Dose-response relationship of MIJ821 with respect response relationship of MIJ821 to change from baseline in MADRS total score at 24 hours after single s.c. injection • Exposure-response relationship of MIJ821 with respect to change from baseline in MADRS total score at 24 hours (Day 2)

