12.5 Analysis supporting secondary objectives

12.5.1 Efficacy and/or Pharmacodynamic endpoint(s)

Duration of antidepressant effect of MIJ821

To assess the efficacy of antidepressant effect of MIJ821 over time, the following secondary endpoints will be evaluated:

- The change from baseline in the total MADRS score at Day 2, 8, 15, 22 and Day 29 visits after s.c. administration will be analyzed using the mixed-effect model for repeated measures (MMRM). This model will include the fixed, categorical effects of treatment, time (i.e. analysis visits), baseline MADRS score, class of anti-depressant standard of care, treatment-by-time and baseline MADRS score-by-time interactions. An unstructured (UN) covariance structure will be used to model the within-subject variability. More details of this analysis will be specified in SAP.
- Number (percentage) of participants who discontinued study due to lack of efficacy or need for new antidepressant treatment (pharmacological or psychotherapy) will be summarized by treatment arms.

Dose-response relationship of MIJ821

The assessment for the dose-response relationship of MIJ821 and estimation of the target dose will be based on the estimated dose-response curve derived from the MCP-Mod methodology in primary analysis (see Section 12.4.2).

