12.5.2 Safety endpoints

For all safety analyses, the safety set will be used. All listings and tables will be presented by treatment group.

Safety summaries (tables, figures) include only data from the on-treatment period with the exception of baseline data which will also be summarized where appropriate (e.g. change from baseline summaries). In addition, a separate summary for death including on treatment and post treatment deaths will be provided. In particular, summary tables for adverse events (AEs) will summarize only on-treatment events, with a start date during the on-treatment period (treatment-emergent AEs).

The on-treatment period will be defined as starting from the date of administration of study treatment plus up to EOS visit.

Adverse events

All information obtained on adverse events will be displayed by treatment group and participant.

The number (and percentage) of participants with treatment emergent adverse events (events started after the study medication or events present prior to start of double-blind treatment but increased in severity based on preferred term) will be summarized in the following ways:

• by treatment, primary system organ class and preferred term.

- by treatment, primary system organ class, preferred term and maximum severity.
- by treatment, Standardized MedDRA Query (SMQ) and preferred term.

Separate summaries will be provided for study medication related adverse events, death, serious adverse events, other significant adverse events leading to discontinuation.

The number (and percentage) of psychotomimetic AEs (dissociation, amnesia, sedation) will be tabulated by treatment group, according to severity and relationship to drug.

The number (and percentage) of participants with adverse event of special interest (AESI) will be summarized by treatment. AESI include risks specified in the safety profiling plan or any other events of interest specific to the project.

A participant with multiple adverse events within a primary system organ class is only counted once towards the total of the primary system organ class.

Vital signs

All vital signs data will be listed by treatment group, participant, and visit/time and if ranges are available, abnormalities will be flagged.

Summary statistics will be provided by treatment group and visit/time. The average blood pressure change over time will be presented by line plot.

12-lead ECG

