### **4 Change to protocol specified analyses**

Not applicable.

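### The SAP omits the protocol's severity-and-relationship table for dissociation, amnesia and sedation, and its Section 4 records neither this nor the other departures

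*SAP*

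**What the plan says.** **Protocol.** The secondary safety endpoint in Table 2-1 is "Incidence and severity of treatment-emergent adverse events (TEAEs), including AEs of special interest", and SAP Table 1-1 repeats it. Protocol 12.5.2 then makes a specific commitment: "The number (and percentage) of psychotomimetic AEs (dissociation, amnesia, sedation) will be tabulated by treatment group, according to severity and relationship to drug". A separate sentence in that section asks for participants with AESIs by treatment, so the two outputs are distinct. The section also asks for AEs by Standardized MedDRA Query (SMQ), a separate death summary, and a summary of "other significant adverse events leading to discontinuation". Protocol 12.5.1 adds, by arm, the "Number (percentage) of participants who discontinued study due to lack of efficacy or need for new antidepressant treatment".

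**SAP.** Section 2.7.1.2 states "AESI will be summarized by risk and by PT for each treatment arm for the on-treatment period", and adds that "the investigator reported AESIs from the eCRF will be summarized similarly by risk and by PT and treatment arms". It also plans times to onset and resolution, dot plots and listings. Neither severity nor relationship appears there. AE severity enters only through the general tables of Section 2.7.1, "by treatment arm, primary system organ class, preferred term and maximum severity", which Table 2-6 marks for all AEs and for all treatment-related AEs. Section 4, headed "Change to protocol specified analyses", holds one entry, saying that the section does not apply.

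**The concern.** The trial is meant to guide dose selection, and these are the tolerability events to weigh against efficacy. Protocol 4.2.1 reports that dissociation became more frequent with dose in the subcutaneous healthy-volunteer study. About 66% of participants had mild to moderate dissociation at 12 mg, and the section gives this as background for a top dose of 10 mg here. A natural question at the end of the trial is how many participants per dose had at least moderate dissociation, and how many of those events the investigator attributed to the drug. The protocol promised a table close to that question, and the SAP does not contain it.

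The second issue is traceability. Someone who relies on SAP Section 4 would conclude that every protocol-specified analysis is carried forward, which is not so.

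**Working it through.** No figure in the plan needs to be reproduced. The check sets the protocol outputs beside the readable SAP text. SAP Section 4 mentions none of these rows.

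| Protocol output | SAP | Noted in SAP history? |
|---|---|---|
| Dissociation, amnesia, sedation by arm, severity, relationship (12.5.2) | AESIs by risk and preferred term, neither split (2.7.1.2) | No, in readable text |
| AEs by SMQ (12.5.2) | Absent | Yes, deleted |
| Separate death summary (12.5.2) | Within SAE outputs (2.7.2) | Yes |
| Lack-of-efficacy discontinuation or new antidepressant (12.5.1) | Discontinuation reasons summarized (2.3.1); new treatment in the intercurrent-event listing (2.4.2.2) | Yes |
| AEs leading to discontinuation (12.5.2) | No row in Table 2-6; reasons in disposition only | No |
| Laboratory shift tables (12.5.2) | Counts of newly occurring and worsening values (2.7.3) | That summary was updated; shift tables not mentioned |
| Summary of overall ECG interpretation (12.5.2) | Findings listed (2.7.4.1.2); abnormal values counted (2.7.4.1.3) | No |

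**Can Table 2-6 stand in for the first row?** Let *a* and *b* be the participants in one arm with an event of at least a given severity under two preferred terms of the same risk. The number with that severity for the risk as a whole lies between max(*a*, *b*) and *a* + *b*, capped at the arm size. Take hypothetical counts *a* = 4 and *b* = 3 in an arm of 14:

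- lower bound: max(4, 3) = 4, and 4/14 = 29%;
- upper bound: 4 + 3 = 7, and 7/14 = 50%.

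If one preferred term carries the whole risk, *b* = 0 and the range shrinks to *a*. The gap therefore matters only where a risk spans several terms.

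The protocol sentence could also be read as counting events and not participants. Table 2-6 would not supply that either, because SAP 2.7.1 counts a participant once within each preferred term.

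**Can the scales stand in?** SAP 2.7.4.3 and 2.7.4.4 summarize CADSS total and component scores, CADSS threshold counts, and any or severe sedation on the MOAA/S, by arm and visit. These are one-per-participant measures of intensity. They are taken at 0.5, 1.5, 4 and 24 hours and then weekly, and the CADSS recall is the current state (Protocol 8.4.4.1), so a peak between assessments can be missed. They carry no causality. Investigator severity (Protocol 10.1.1) grades interference with normal activities, which is a different quantity.

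**The case against.** The strongest reply is that severity and relationship by dose are planned. Table 2-6 gives maximum severity for all AEs and for treatment-related AEs, term by term, and the protocol sentence does not explicitly ask for a de-duplicated count per risk. The scales add participant-level intensity, and AESI listings by arm allow a hand count. The study is non-confirmatory, with about 3 × 14 = 42 active participants and descriptive safety tables. All of this stands, and it keeps the point small. It does not supply the grouped table that the protocol names.

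A reader might infer more than the documents support:

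- **That severity by dose goes unreported.** It is reported at preferred-term level.
- **That the proof-of-concept AE terms prove several terms per risk.** Amnesia, somnolence and depersonalization/derealization disorder fall naturally into three different risks. No document assigns feeling abnormal to any of them.
- **That the by-arm count of lack-of-efficacy discontinuations is lost.** SAP 2.3.1 still summarizes the reasons for early discontinuation, and SAP 2.1 makes presentation by arm the default. What is reduced to a listing is the need for new antidepressant treatment.
- **That changes were concealed.** The document history records the SMQ, death and discontinuation/new-treatment changes with brief reasons. The fault there is that Section 4 does not match it.

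**Conclusion.** The point holds as a conflict between protocol and SAP on a stated secondary endpoint. The committed severity-and-relationship tabulation of dissociation, amnesia and sedation is missing at the level of the grouped risk, without disclosure in any readable text, and Section 4 is inaccurate. The primary test is untouched. The practical loss runs from almost nothing, if each risk is coded to one preferred term, to a range such as 4 to 7 of 14 in the illustration.

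Two assumptions apply. First, redaction does not hide the table: SAP 2.7.1 to 2.7.2 show no redaction marks. Second, the output shells and the AESI search strategy, which are not available here, do not already add the two splits. If they do, the SAP text still needs to say so.

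**What to change.** 1. In SAP 2.7.1.2, add maximum severity and relationship to the by-arm AESI-by-risk table, for dissociation, amnesia and sedation, counting each participant once per risk.
2. In SAP Section 4, replace the present entry with a list of every departure from the protocol-specified analyses, each with its reason. Include the SMQ summary and the separate death summary. State that the need for new antidepressant treatment now appears only in a listing, and that AEs leading to study discontinuation have no preferred-term table. Confirm whether the laboratory shift tables and the ECG interpretation summary were dropped on purpose, and list them if so.

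The cost is one small table from data already collected, plus SAP wording.

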### 2.7.2 Deaths

Deaths (if any) will be summarized and listed under SAE by actual treatment arm.

### 2.7.3 Laboratory data

Both of raw measures and change from baseline of laboratory results (hematology, blood chemistry) will be summarized by treatment arm and analysis visit.

The clinical abnormality is defined as out of the normal ranges defined in the laboratory specification document. The newly occurring and worsening events are defined by comparing the measured laboratory parameters at baseline and post-baseline with the lower and/or upper limits of the normal ranges (see [Table 2-8](#)). In addition to the normal ranges, some of the lab parameters, which are covered by the Common Terminology Criteria for Adverse Events (CTCAE) version 5.0, will also be graded using the Novartis internal validated macro (with details covered in PDS) and the newly occurring and worsening events are also defined in [Table 2-8](#). The number and proportion of participants with newly occurring or worsening laboratory parameters based on normal ranges and CTCAE grades (if applicable) will be summarized by treatment arms and by visits (24 hours post-dose and EOS).

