Given that MIJ821 may impair the mental or physical abilities required for the performance of potentially dangerous tasks such as driving a car or operating machinery, participants should be advised about these potential risks. If the participant is feeling drunk or dizzy or if he/she experiences visual disturbances, hallucinations, or euphoric mood, then he/she should not drive, use machines or perform any other tasks that require his/her attention and good coordination. In case of a safety concern, the participant should be hospitalized (or hospitalization should be

Page 36 of 104 Protocol No. CMIJ821B12201

prolonged) as per investigator's judgement until resolution of these events or absence of a safety risk.

• Respiratory effects

MIJ821 demonstrated an increase in respiration rate of 23% at 3 mg/kg in the rat FOB/respiratory safety pharmacology study. However, ketamine might have a negative impact on respiratory function when administered rapidly, particularly at high doses. Ketamine at anesthetic dosages is considered relatively safe because protective airway reflexes are preserved. There are no reports of respiratory distress with ketamine i.v. at dosages of 0.3-0.5 mg/kg with 40 minute infusions that have been administered in depression participants. In the PoC study, no specific respiratory effect related signal was noted.

Respiratory effects will continued to be assessed in the study using adverse event data.

• Cystitis or other lower urinary tract adverse events.

Cases of ulcerative or interstitial cystitis have been reported in individuals with long-term off-label use or misuse/abuse of ketamine. In clinical studies with Spravato (esketamine) nasal spray, there was a higher rate of lower urinary tract symptoms (pollakiuria, dysuria, micturition urgency, nocturia, and cystitis) in Spravato treated participants than in placebo-treated participants. No cases of esketamine-related interstitial cystitis were observed in any of the studies, which included treatment for up to a year.

Cystitis and other urinary symptoms will be monitored in the current study by AE collection and urinalysis.

• Injection site reactions and hypersensitivity

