Hematology	Hemoglobin, hematocrit, red blood cell count, white blood cell (WBC) count with differential (e.g., neutrophils, basophils, eosinophils, monocytes, lymphocytes), other (absolute value preferred and percent) and platelet count will be measured.
Chemistry	Albumin, alkaline phosphatase, total bilirubin, bicarbonate, calcium, Total cholesterol, low density lipoprotein (LDL), high density lipoprotein (HDL), chloride, creatinine (Glomerular Filtration Rate to be calculated based on the Cockcroft-Gault formula), creatinine kinase (CK), Gamma-glutamyl transferase (GGT), glucose (fasting), lactic dehydrogenase (LDH), phosphorus, lipase, amylase, magnesium, potassium, total protein, AST, ALT, sodium, triglycerides, blood urea nitrogen (BUN) or Urea, uric acid, C-reactive protein (high sensitivity). If the total bilirubin concentration is increased above 1.5 times the upper limit of normal, direct and indirect reacting bilirubin should be differentiated. Thyroid Stimulating Hormone (TSH) level will be analyzed as well. In case of clinically relevant abnormal TSH value, additional evaluation will be performed (free triiodothyronine [fT3] and free thyroxine [fT4]).
Urinalysis	A midstream urine sample (approx. 30 mL) will be obtained, in order to avoid contamination with epithelial cells and sediments, and allow proper assessments. A semi-quantitative "dipstick" evaluation for the following parameters will be performed: specific gravity, pH, glucose, protein, bilirubin, urobilinogen, ketones, leukocytes and blood. If the dipstick result is positive for protein, leucocytes and/or blood, the sample will be sent for microscopic analysis of WBC, RBC and casts. Furthermore the protein-creatinine ratio (PCR) and the albumin-creatinine ratio (ACR) might also be measured
Coagulation	Prothrombin time/International normalized ratio (PT/INR), Activated partial thromboplastin time (APTT)
Alcohol / Drugs of Abuse*	Breathalizer / Dipstick
Pregnancy Test and Assessment of Fertility	Serum / Urine pregnancy test (as outlined in Section 8.4.3)

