10.2.5 Adverse events of special interest

Based on the current available information, considering the ketamine safety profile and clinical/non-clinical evidence available for MIJ821, following events are considered AESI. This information is subject to change, based on the availability of incremental clinical experience with MIJ821. Please refer to the current Investigator Brochure for the most updated information on safety profile.

- Dissociation
- Sedation
- Cardiovascular effects (BP changes and QT interval prolongation on ECG)
- Respiratory effects (difficulty in breathing, changes in oxygen saturation)
- Suicidality (suicidal ideation or behavior)
- Memory gaps/ amnesia
- Cystitis or lower urinary tract adverse events

The list of current adverse events of special interest is available in the IB.

Post dose observation / Hospitalization

A four-hour post-dose observation period is implemented in this trial to ensure patients' safety and give required time for the potential events of interest to onset. Most of the events of interest should also be resolved by the end of the suggested observation period. The adverse events of interest should be followed up on site until resolution or until absence of safety risk assessed by the investigator based on clinical evaluation and judgement. If severe dissociative, psychotic, suicidal, sedative, cardiovascular or agitated symptoms emerge, it is recommended investigators hospitalize participants until those adverse events are resolved. If they persist, or based on clinical judgment or patient preference, those participants can be discontinued from the study at any time.

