All ECG data will be listed by treatment group, subject and visit/time; abnormalities will be flagged.

The overall interpretation of the ECGs will be summarized by treatment group and visit/time.

Any clinically significant changes in ECG parameters will be summarized by treatment group.

Summary statistics will be provided by treatment and visit/time.

Clinical laboratory evaluations

Notable abnormal laboratory data will be listed by treatment group, participant and visit if ranges are available.

All laboratory data will be summarized by treatment group, and visit/time. Shift tables using the low/normal/high/ (low and high) classification will be used to compare baseline to the worst on-treatment value.

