**Table 5-2 Renal abnormality criteria**

Criterion
Serum creatinine increase $\geq 25\%$ and $< 50\%$ compared with baseline
Serum creatinine increase $\geq 50\%$
New onset dipstick proteinuria $\geq 3+$ OR Protein-creatinine ratio (PCR) $\geq 1\text{g/g Cr}$ (or $113\text{ mg/mmol Cr}$ equivalent as converted by the measuring laboratory)
New onset hematuria $\geq 3+$ on urine dipstick

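### SAP 2.7.3 leaves urinalysis out of the laboratory summary and drops the shift table that protocol 12.5.2 promises, so by-arm tabulation of dipstick changes below 3+ is not assured

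*SAP*

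**What the plan says.** **Protocol**

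- Section 10.2.5 puts "Cystitis or lower urinary tract adverse events" on the list of adverse events of special interest (AESI).
- Section 4.5 states how they are followed: "Cystitis and other urinary symptoms will be monitored in the current study by AE collection and urinalysis".
- Table 2-1 counts urinalysis among the secondary safety endpoints ("standard safety assessments such as vital signs, ECG, hematology, blood chemistry, urinalysis"). SAP Table 1-1 repeats this.
- Table 8-1 marks urinalysis for entry in the clinical database at screening, pre-dose on Day 1, 24 hours and Day 29.
- Table 8-3 describes a semi-quantitative dipstick covering "specific gravity, pH, glucose, protein, bilirubin, urobilinogen, ketones, leukocytes and blood". Samples positive for protein, leukocytes or blood go to microscopy.
- Section 12.5.2 sets the reporting scope: "All laboratory data will be summarized by treatment group, and visit/time". It adds shift tables, on a low/normal/high classification, from baseline to the worst on-treatment value.

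**SAP**

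- Section 2.7.3 says that raw measures and "change from baseline of laboratory results (hematology, blood chemistry) will be summarized by treatment arm and analysis visit".
- The same section adds counts, by arm and by visit (24 hours and end of study), of newly occurring or worsening laboratory parameters. These use normal ranges and, where applicable, CTCAE grades, under the rules of Table 2-8. It also lists by arm the participants with such abnormal values.
- Table 5-2 gives renal criteria. The dipstick rows are protein of 3+ or more (with a protein-creatinine ratio alternative) and "New onset hematuria" of 3+ or more.
- Section 4, on changes to protocol-specified analyses, reads "Not applicable".

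**The concern.** The protocol names two monitors for the urinary AESI: adverse event reporting and urinalysis. It promises group-level summaries and shift tables for every laboratory category. The SAP's descriptive summary covers two categories and leaves out the one tied to this AESI. The shift table is missing for every category, and nothing in SAP Section 4 tells a reader that the scope was reduced.

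What is at stake is whether a dose-related drift in dipstick leukocytes, blood or protein, short of a renal alert and short of a reported adverse event, would be visible in a table by dose. As the SAP stands, that depends on classification rules it does not give.

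**Working it through.** No sample size, error rate or effect estimate is involved, so this is a comparison of texts.

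**1. Scope, side by side**

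| Item | Protocol 12.5.2 | SAP 2.7.3 |
|---|---|---|
| Summary by group and visit | all laboratory data | hematology and blood chemistry |
| Shift, baseline to worst value | yes (low/normal/high) | none specified |
| Newly occurring/worsening counts | not mentioned | yes, by visit, no category restriction |
| Listing of abnormal values | notable abnormal values, if ranges are available | newly occurring or worsening values, by arm |
| Departure declared | – | none in Section 4 |

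The newly occurring/worsening counts are the nearest substitute for the shift table. They are made visit by visit, not on the worst post-dose value.

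**2. Do the substitute rules fit a dipstick?**

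- *Normal-range rules (Table 2-8).* These compare a value with the lower and upper limits of normal. Worsening requires the value to lie beyond a baseline that is already out of range. That works for numeric items such as specific gravity and pH. For negative, trace, 1+, 2+ and 3+, the SAP does not say which category counts as the upper limit or how the categories are ordered.
- *CTCAE rules.* SAP 2.7.3 says that some laboratory parameters are graded. SAP 5.3 says that most are, and names urinalysis among the categories. Neither lists the urinalysis items. The details are left to the programming specification.
- *Table 5-2.* SAP 2.7.3 introduces it for hepatic and renal signals. It has no leukocyte row, and its dipstick rows for blood and protein start at 3+.

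**3. One illustrative participant**

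Take a participant who is negative at baseline and has 2+ leukocytes and 2+ blood at 24 hours.

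| SAP output | Counted or shown? |
|---|---|
| Descriptive laboratory summary | No; urinalysis is outside the stated scope |
| Table 5-2 counts | No for these two results: no leukocyte row, and 2+ is below 3+ |
| Newly occurring counts, normal range | Only if the laboratory specification gives these items a range such as negative |
| Newly occurring counts, CTCAE | Only if the grading macro covers these items |
| By-arm listing of abnormal values | Yes, once the result is classed as newly abnormal |
| AE and AESI tables (SAP 2.7.1) | Only if reported as an adverse event |

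Two outputs exclude this participant by their wording. Whether either by-arm laboratory count includes the participant cannot be determined from the SAP.

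**4. Context only**

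With 14 per arm (protocol 12.8.1), zero observed shifts in an arm would bound the true rate, one-sided 95%, at 1 − 0.05^(1/14) = 0.193, about 19%. The information per arm is thin with or without the table, and this figure does not measure the gap.

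**The case against.** The strongest reply is that urinalysis is not lost. The parenthesis in SAP 2.7.3 qualifies only the raw and change-from-baseline summary. The newly occurring/worsening counts carry no such limit, and SAP 5.3 names urinalysis for grading. If the laboratory specification takes negative as the normal result, a 2+ finding is counted as newly occurring. Parameter-level detail is delegated to the laboratory specification, the programming specification and the table shells, none of which is available here. All of this stands. It is why the conclusion is that tabulation is not assured, rather than that it is absent.

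Three stronger readings are tempting, and the documents do not support them:

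- *Only 3+ dipstick findings are counted.* That describes the dipstick rows of Table 5-2 alone. The same table also counts a raised protein-creatinine ratio, and the Table 2-8 counts can include lesser changes.
- *The urinalysis data do not reach the report.* SAP 2.7.3 lists by arm every participant with a newly occurring or worsening abnormal laboratory value. With about 14 per arm, such a listing can be read by dose.
- *Only volunteered adverse events remain.* Protocol 10.1.1 has events sought by questioning at each visit, allows detection through laboratory findings, and makes clinically significant abnormal results adverse events. SAP 2.7.1.2 then tabulates AESIs by risk, preferred term and arm, from both the search strategy and the investigator reports.

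Two more points stand. The protocol's shift table uses low/normal/high, so a table by dipstick category would be an ordinal counterpart of it, not the same table. And this is a single-dose study, while protocol 4.5 links the ketamine cystitis cases to long-term use or misuse, which limits the practical weight.

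The reply does not remove the scope mismatch. A listing is not a summary by group, AESI tables show only reported events, and the SAP sets out no ordinal rule for a listed secondary safety measure.

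**Conclusion.** The point holds as a minor matter of reporting scope. The SAP narrows the descriptive laboratory summary to two categories and carries over no baseline-to-worst shift table. The protocol promises both for all laboratory data, and Section 4 of the SAP records no departure. The remaining routes by which urinalysis could be tabulated rest on rules that do not clearly classify ordinal dipstick results, so by-arm counts of leukocyte changes, and of blood or protein changes below 3+, are not assured.

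The conclusion on scope rests only on visible text. The conclusion on tabulation assumes that the unseen specifications do not already define dipstick categories for Table 2-8. If they do, what remains is the undeclared departure from protocol 12.5.2. No efficacy result, error rate or clinical management rule is affected.

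**What to change.** Preferred: in SAP 2.7.3, add urinalysis and coagulation to the summaries by arm and visit. For dipstick leukocytes, blood and protein, add a shift table by arm from baseline category to worst post-dose category, as the ordinal counterpart of the protocol's low/normal/high table. Placing it beside the cystitis/lower urinary AESI counts would let the two monitors be read together.

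Otherwise: name the urinalysis parameters and the ordinal cut-offs used under Table 2-8, and state in SAP Section 4 that the summary scope and shift tables differ from protocol 12.5.2.

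Cost: one or two extra tables from data already in the clinical database, or a short text change. No new assessments are needed.
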